The assessment battery takes 15 minutes to complete on average based on the use of a similar question battery with an adolescent population in other studies. Each young person will be supported during completion, at baseline by staff in the services and at 6- and 12-month by researchers who will be blind to participant allocation. Research staff will provide training in baseline data collection to staff in Bridgend across the five services through an interactive in-person training session and this will include a training manual and on-going support. At the end of each assessment point and at the end of any qualitative interview the young person will be provided with an opportunity to debrief and reflect on the impact of answering the questions. This debrief is designed to identify any negative impacts of reflecting on themselves and any potential re-traumatisation. If issues are identified, the potential adverse event standard operating procedure will be activated, and trauma leads in each service asked to conduct an assessment and provide any necessary intervention. All adverse events in both arms of the study will be recorded and reported.

In addition to key demographics (age, sex, ethnicity, and IMD) that will be assessed at baseline we will assess the exposure to adverse child experiences assessed on entry to the service using existing records.

Six months after randomisation, in both arms of the study, young people will be contacted by phone or email by researchers and asked to complete the short revised therapeutic alliance scale for children (TASC-r; (Shirk and Saiz, 1992)), this assesses the quality of the relationship between the young person and staff member. Therapeutic alliance is a strong predictor of outcome, and this will be used in the prognostic model (objective 5).

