### **Analysis**

The proposed analysis is covered in depth in the associated statistical analysis plan.

Objective 1: Participant flow through the study will be presented as a CONSORT diagram. We will present demographics and outcome variables for each group at each time-point. We will explore the validity of the randomisation procedure by presenting baseline outcomes and estimates of precision by allocated group.

Objective 2: The primary outcome is the mean difference between BAU and RBT in number of offences over the 6 months from baseline, assessed using the SRDS at 6-months. The analysis will be conducted using an analysis by intention to treat (ITT) and will include all available data with participants maintained as members of their allocated group, irrespective of whether they complied with the intervention or not. Data will be assessed for distributional assumptions and will probably take the form of a generalised linear regression model, adjusted for baseline stratification covariates and baseline SRDS score. Both the intervention and control vary by service, with a higher to lower hierarchy of complexity running from youth justice, edge of care, children's services, youth development to early help. What is delivered in both the intervention and control group is tailored to the young person's needs. While we

can describe the variety of different sessions delivered in our results, we cannot completely account for it in the analysis, nor can we adjust for any potential contamination due to multi-agency working. Instead, we take a holistic approach, seeing what is delivered as a whole, rather than the sum of its individual parts. Though as complexity is hierarchical across services, we will adjust the analysis for service. This provides the best estimate of effect of how the intervention is proposed to be implemented across diverse services and as a rigorously designed RCT any potential errors introduced will be equally distributed across both groups and mitigated in the analysis. We will apply a multi-level model allowing for participants to be nested within services as a fixed effect. Results will be presented as a mean difference and associated 95% confidence intervals. A secondary analysis will be conducted using a similar approach at month 12.

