Secondary outcomes will be assessed in a similar way by establishing diagnostic plots to identify the most appropriate regression approach; logistic for dichotomous outcomes, ordinal for ordered categorical outcomes, linear for continuous outcomes and fractional for proportions. Stratification factors and baseline covariates will be included within the model.

If the missing data exceeds 5%, sensitivity analyses will be performed using a pattern mixture approach and multiple imputation to compare the sensitivity of conclusions to varying assumptions about the missing data, particularly whether data is missing at random (MAR) or missing not at random (MNAR). This allows for an assessment of both random and systemic bias. Results based on complete data analysis, MAR and MNAR will be presented to explore the influence of missing data on outcomes observed.

We will conduct a Complier Average Causal Effects (CACE) analysis using an instrumental variable framework to explore the impact of compliance on the primary outcomes at different levels of compliance, both fidelity to the steps involved in each tier and quintiles of compliance. CACE weights the analysis by the ITT treatment effect by the proportion of compliance, this allows the estimation of unbiased treatment effects and maintains the allocation in the analysis.

Objective 3: For staff we will explore the differences between the groups in terms of overall wellbeing, perceptions of working in a trauma informed manner and confidence in working with young people who have experienced adverse childhood experiences derived from the SWEMWBS and ARTIC questionnaire at months 6 and 12 using linear regression adjusted for baseline score and service. Staff turnover and proportion absence will be assessed in a similar manner using fractional regression.

Objective 5: Stepwise regression analysis will be performed to model the relationship between pre-randomisation factors and demographics, on observed outcomes at 6 months.

Interaction terms with allocation arm will be included in the analysis, and a significance level of 0.1 will be used to determine which factors are to be included in the regression model. Pre-randomisation factors will include sex, age, ethnicity, IMD, family cohesion, adverse childhood experiences assessed by the service, and process measures, staff perceptions, staff confidence, and therapeutic alliance. The allocated arm will be included in this analysis as an interaction term.

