The primary outcome relates to the participant and is the quantity of self-reported delinquent acts in the six months after randomisation assessed using the SRDS. The quantity of delinquent acts is calculated as the sum of positive endorsements for each of the nineteen questions in the SRDS. Two datasets will be created for statistical analysis, the primary analysis will be based on the intention to treat (ITT) dataset. The secondary analyses will examine intervention effects under different scenarios for compliance with allocation (see compliance section below): complier average causal effects (CACE); and per protocol (PP).

The ITT dataset contains all available data for participants who were randomised, regardless of whether they complied with allocation. This dataset will include participants who were withdrawn/withdrew from the trial post-randomisation. These analyses are a lower bound estimate of intervention effects as they represent the effect of offering an intervention, rather than the effect of receiving the intervention.

The primary outcome is the quantity of offences at 6-months post-randomisation. We expect the primary outcome will take the form of a linear distribution. Prior to analysis we will conduct a series of diagnostic tests and assess the underlying assumptions prior to choosing an appropriate and statistically rigorous regression approach. The analysis will take the form of an analysis of covariance using a linear regression. Models will be adjusted by baseline values, quantity of offences in the six months prior to randomisation and stratification factors, service, age group and sex, as covariates. The regression model specification is as follows (eq.1):

$$SRDS6_{i,j} = \alpha + \beta_1(allocation)_{i,j} + \beta_2(SRDS0)_{i,j} + \beta_3(sex)_{i,j} + \beta_4(age)_{i,j} + \beta_5(service)_j + \varepsilon_i$$

Where for participant i within service j ; $SRDS6$ is the 6-month SRDS score, $allocation$ is the allocated group, $SRDS0$ is the baseline SRDS score, sex is the participant sex, age the age group, $service$ the service level dummy variables to adjust for fixed effects and ε_i the individual level error.

An estimate of difference will be generated as a mean difference between the groups and the associated 95% confidence interval.

Secondary outcome analysis

For participants the quantity of offences reported at 12-months will be analysed using similar methods as 6-months (eq. 2).

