To explore the role of compliance on outcomes we will conduct a Complier Average Causal Effects analysis (CACE). The definition of compliance with allocation for this trial is as follows (see Table 1 below): (i) those who receive trauma screening (TS) and 80% of RBT interventions offered will be considered 'compliers' in the intervention group (cell A); (ii) those in the control group who did not receive any RBT intervention (cell D). In the intervention group, those attending no trauma screening and/ or less than 80% of interventions offered will be considered 'non-compliers', (cell B). All non-compliers in the intervention group are regarded as being 'contaminated' because they received the control condition (no RBT interventions). For the control group, there is no option for control participants to access the intervention, so there cannot be non-compliance hence this is n/a (cell C).

To further explore the role of compliance on outcomes we will create several thresholds for intervention compliance;

1. TS versus no TS.
2. TS and/ or < 20% of RBT interventions versus TS and >= 20% RBT.
3. TS and/ or < 40% of RBT interventions versus TS and >= 40% RBT.
4. TS and/ or < 60% of RBT interventions versus TS and >= 60% RBT.
5. TS and/ or < 80% of RBT interventions versus TS and >= 80% RBT.

CACE analysis will be undertaken for each threshold and presented as a sensitivity analysis to allow a comparison of outcomes, (RBT group vs BAU) at different thresholds of compliance.

Table 1: Compliance/non-compliance according to group allocation versus intervention received.

	Actually received...	
Allocated to... ↓	Intervention	Control
Intervention	
A. Intervention complier
 
Meeting the stated threshold
	
B. Intervention non-complier
 
Not meeting the stated threshold

Control	
C. Control non-complier
 
n/a
	
D. Control complier
 
Control group participant

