We will assess intervention effects in the presence of non-compliance, with compliance measured at the individual level and including all those allocated as part of the trial. Our approach for assessing intervention effects under non-compliance will be via the instrumental variable framework (IV). The benefit of using an IV approach is that randomisation is maintained in the analysis, which is crucial for estimating unbiased intervention effects. In summary, with a binary measure of compliance CACE weights the analysis by treatment allocated (ITT) intervention effect by the proportion of compliers (eq. 5):

$$CACE = ITT / \textit{proportion compliant}$$

If the proportion compliant is 1.0 (i.e. perfect compliance) then the CACE estimate is the same as the ITT estimate, but otherwise the impact of this approach is to increase the magnitude of the intervention effect.

CACE uses a two-stage least squares (2SLS). The first stage model uses intervention received (T) as the outcome, with random allocation (Z) as the independent variable (eq. 6):

$$T = \alpha + Z$$

Based on the stage 1 model, we then calculate predicted values of intervention received (\hat{T}) for use in stage 2. The second stage model predicts the substantive outcome (Y e.g. quantity of offences) using the predicted values of intervention received (\hat{T}) based on the stage 1 model (Eq.7):

$$Y = \alpha + \hat{T} + \varepsilon$$

An additional sensitivity analysis will employ a per protocol approach (PP), containing all data for participants who complete the trial as planned – in intervention and control groups - without any major protocol violations or exclusions. PP analysis essentially drop those individuals who have not strictly complied with their allocation – both those who only partially complied with their allocated intervention and those who did not receive their allocated intervention. This means that PP represents a likely ‘best case scenario’ for intervention effect estimation. The PP dataset will be analysed in a similar manner to the ITT dataset.

Presentation of outcomes

As the sample is large, effect size differences will be calculated using Cohen’s d, specified in the following equation (eq. 8):

$$\delta = (Y_i - Y_o) / S$$

Where Y_i and Y_c are the regression adjusted means, derived from eq. 1, for the intervention and control groups respectively and S is the pooled standard deviation.

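### Exposure of BAU participants to RBT is not balanced by randomisation, and the CACE should use observed receipt in both arms instead of presetting control receipt to n/a

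*Protocol*

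**What the plan says.** **Protocol, Analysis, Objective 2.** The text explains that delivery varies by service and need in both arms and cannot be fully modelled, "nor can we adjust for any potential contamination due to multi-agency working". It then reassures the reader that, in a rigorous RCT, "any potential errors introduced will be equally distributed across both groups and mitigated in the analysis". The sentence covers tailoring and service differences, but contamination has just been named and falls within it.

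**SAP, Primary outcome analysis.** On the ITT dataset: "These analyses are a lower bound estimate of intervention effects as they represent the effect of offering an intervention". The reason given is offer versus receipt; exposed controls are not mentioned.

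**SAP, Compliance.** Control compliers are "those in the control group who did not receive any RBT intervention (cell D"). Control non-compliance is then ruled out: "there is no option for control participants to access the intervention, so there cannot be non-compliance hence this is n/a (cell C"). Equation 5 divides ITT by the proportion compliant: "CACE weights the analysis by treatment allocated (ITT) intervention effect by the proportion of compliers". Equations 6 and 7 give the two-stage least squares form, with intervention received (T) regressed on allocation (Z).

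**Protocol, Analysis.** On CACE: "this allows the estimation of unbiased treatment effects and maintains the allocation in the analysis". The Research Methods section of the process evaluation also calls the resulting estimate unbiased.

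**The concern.** Randomisation balances what exists at allocation. Exposure of controls to RBT comes later and can occur in the BAU arm only, so there is nothing in the other arm to offset it. If RBT reduces offending, exposed controls offend less and the difference shrinks. Nothing in the primary model mitigates this, as the Protocol's own preceding sentence concedes.

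The CACE is where non-compliance is meant to be handled, but presetting cell C to n/a removes the control-arm term. The cell D definition means something only if receipt by a control is possible, and no specified step checks whether it occurred. The Protocol's Compliance section assesses component fidelity in the RBT arm only; dose in both arms is meeting attendance, not RBT content.

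At stake are the reading of a small or null primary result (RBT does not work, or BAU received part of it) and a secondary estimate described as unbiased when it rests on an unchecked zero.

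**Working it through.** **The plan's own figure.** Inputs from Protocol, Sample size calculations: standardised difference 0.25, two-sided alpha 0.05, power 80%, 1:1. The normal approximation gives 2 × (1.960 + 0.842)² / 0.25² = 251.2, so 252 per arm. The t-test version gives 252.13, so 253 per arm and 506 in total, as stated. Then 506 / 0.9 = 562.2, against the stated 562. Power at 253 per arm is 80.3% (normal approximation). The sample size reproduces and makes no allowance for contamination.

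**CACE with control receipt.** Let p be the proportion meeting the receipt definition in the RBT arm, c the proportion meeting it in the BAU arm, and δ the effect of receipt in compliers. Assume no benefit below the definition, and that nobody receives RBT only because they were allocated to BAU. Then:

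- ITT = δ(p − c)
- Equation 5 with cell C at n/a: ITT / p = δ(p − c) / p, an understatement of c/p
- With observed receipt in both arms: ITT / (p − c) = δ

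The documents give neither p nor c; both are assumed below, with δ = 0.25.

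| p | c | ITT | ITT/p | Understatement | ITT/(p − c) |
|---|---|---|---|---|---|
| 80% | 5% | 0.1875 | 0.234 | 6% | 0.25 |
| 80% | 10% | 0.175 | 0.219 | 12.5% | 0.25 |
| 80% | 20% | 0.150 | 0.188 | 25% | 0.25 |
| 60% | 10% | 0.125 | 0.208 | 17% | 0.25 |
| 60% | 20% | 0.100 | 0.167 | 33% | 0.25 |

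A simulation of 2,000,000 participants with p = 80%, c = 10% and a true effect of −0.25 gave ITT −0.175, ITT/p −0.219 and, with observed receipt, −0.250.

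**The bias in the other direction.** The SAP treats RBT participants below the threshold as having received the control condition. If they gain a share f of the benefit, ITT = δ(p + (1 − p)f − c). With f = 0.5 (also assumed):

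- p = 80%, c = 10%: ITT = 0.25 × (0.8 + 0.1 − 0.1) = 0.20. ITT/p = 0.25, which is correct by cancellation; ITT/(p − c) = 0.286.
- p = 60%, c = 10%: ITT = 0.25 × (0.6 + 0.2 − 0.1) = 0.175. ITT/p = 0.29; ITT/(p − c) = 0.35.

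So at the percentage thresholds, correcting the divisor alone can move the estimate further from the truth. Threshold 1 (screened or not) is less exposed to this problem, and its definition is the same in both arms.

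**ITT power, illustrative only.** Take 0.25 as the effect with no control exposure (the Protocol does not say this), and let a share c of controls gain full benefit, so that d = 0.25(1 − c). At 253 per arm, power is 76%, 72% and 61% for c = 5%, 10% and 20%.

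**The case against.** The best reply is that control receipt is unlikely and the plan already limits it. Young people go to staff of the matching arm, and YOT staff already trained in RBT are not eligible (Protocol, Randomisation). Youth justice controls see untrained staff only (Protocol, Participants). BAU contains no trauma screening (Protocol, Intervention). This stands: full receipt may well be rare. It does not justify fixing receipt at zero without looking, when trauma leads are service managers and referral assessors charged with spreading the approach in services that deliver both arms.

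Second, a reader might infer that the two documents flatly contradict each other. They need not. The Protocol speaks of diffuse exposure through multi-agency working, and the SAP of access to RBT as defined for compliance. Both can be true. For the same reason, diffuse exposure may leave cell C at or near zero, and no CACE correction will capture it.

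Third, the 2SLS structure already accepts receipt by controls, and dose records and the by-arm ARTIC comparison give some descriptive basis for interpretation. This is right, and it makes the change small: only the preset has to go.

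Fourth, a reader might infer that the post-assessment debrief delivers RBT to controls, because it has "trauma leads in each service asked to conduct an assessment and provide any necessary intervention". It is a safeguarding step, and the Protocol does not say that it includes RBT components.

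**Conclusion.** The Protocol sentence is wrong as applied to contamination, and the n/a in cell C should be replaced by observation. If a proportion c of controls receive RBT, the planned CACE is too small by c/p from this cause: 6% to 25% at p = 80% and c of 5% to 20%, all assumed values.

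A reader might go further and infer that the CACE will be too small overall. The documents do not support that. They give no receipt rate, and partial benefit among RBT participants coded as non-compliers biases the estimate upwards; with half benefit at p = 80% and c = 10% the two cancel. The net direction is uncertain, which is itself enough to qualify the Protocol's claim that the estimate is unbiased.

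Nor do the documents support the inference that the ITT analysis is invalid or the trial underpowered. ITT estimates the effect of allocation as delivered, and the power figures rest on an assumed exposure rate and an assumed meaning of 0.25. The weight of the point lies in a false reassurance and an unchecked input to a secondary analysis.

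**What to change.** 1. **Protocol, Analysis, Objective 2.** Replace the sentence with wording to this effect: *Variation in delivery is part of the comparison. Exposure of BAU participants to RBT is not balanced by randomisation and, if RBT works, would bias the difference towards no effect.* Qualify the claim of unbiasedness for CACE here and in Research Methods.

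2. **SAP, Compliance.** Replace n/a in cell C with the observed number of controls with recorded RBT components: trauma screening, formulation meeting, RBT sessions. Possible sources are the shared contact records (Protocol, Compliance), the component session data (Table 4, IPE.Q1) and the case activity logs (Cost data), extended to BAU cases where they are not already covered. Code T in equation 6 from observed receipt in both arms, so that the equation 5 divisor becomes RBT receipt minus BAU receipt. Make the trauma-screening threshold the main two-sided version. At the percentage thresholds, report control receipt descriptively and note that the estimate assumes no benefit below threshold. A share of sessions offered has no like-for-like meaning in controls: one who attends the only recorded session would score 100%.

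3. **Reporting.** Show control receipt by service alongside the primary result, and state that a small or null difference will be read with it.

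If cell C is zero, the SAP's CACE is unchanged. The primary model, the sample size and the debrief safeguarding rule stay as they are. The cost is some data extraction for BAU cases and, if cell C is not zero, a less precise CACE. At p = 80% and c = 10% the divisor falls from 0.80 to 0.70, so the interval widens by about 0.80 / 0.70 − 1 = 14%, treating the receipt proportions as known.

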### Longitudinal follow-ups

Participant data will be collected at baseline (prior to randomisation) and again at 6- and 12-months post randomisation. Our primary endpoint will be the 6-month post-randomisation date, to meet the deadline for a report in September 2025. We will conduct a secondary analysis using 12-month outcomes to provide longer term effects using the strategies highlighted above. Core outcomes and the time of data collection are presented in table 3.

**Table 3: Core outcomes and time of collection**

Outcome	No of items	Baseline	Six months	Twelve months
Primary				
Self-reported delinquency (SRDS) 	36	✓	✓	✓
Secondary				
Strength and Difficulties (SDQ) 	25	✓	✓	✓
Wellbeing (SWEBWMS)	7	✓	✓	✓
Psychological Distress (GHQ12)	12	✓	✓	✓
Family environment (BFRQ)	16	✓	✓	✓
Receipt Inventory (CSRI)	8	✓	✓	✓
Staff attitudes to trauma informed care (ARTIC)	35	✓	✓	✓
Staff wellbeing (SWEBWMS)	7	✓	✓	✓
Staff turnover & absence	2	✓	✓	✓
Exploratory				
Adverse childhood experiences (ACE-Q)	10	✓		
Process				
Therapeutic relationship	12		✓	
Proportion of sessions planned & delivered	1		✓	✓

SRDS and SDQ are YEF core outcomes.

